#### 2.3.4.3.2 Evaluation system

The nutritional profile can apply specific criteria to evaluate the nutrient content in food by groups or use the same for all. Final score must balance nutrients to promote and limit. This can be achieved by a subtraction or quotient between the two types of nutrients. An example of a balanced algorithm is the Nutrient Rich Food Index [39], where the final score of the food is the result between the score of the nine nutrients to promote and the three nutrients to limit (Chart 1). Later, each food is assigned to a category of a scale of five categories based on this rating.

Another example is the nutritional profile, currently under development, from FSANZ, a derive from the UK FSA profile. This nutritional profile evaluates food to promote (% of fruits, vegetables, nuts, protein and fiber) and limit (energy, saturated fat, total sugars and sodium), giving a score to each one of them.

## 3 RESEARCH QUESTION

---

What FoPNL system has the best acceptability and understanding for healthy food selection in Mexican population?

## **4 JUSTIFICATION**

---

Front of pack nutritional labeling is a strategy that can contribute to increase healthy food choices among consumers and nutritional quality of foods through product reformulation [42,43]. Front of pack labelling is particularly relevant in countries like Mexico, where more than 80% of the burden of deaths is attributed to chronic diseases [44]. Despite the former, the front of pack labeling system used in Mexico is not the most adequate for our population.

Per the latest National Health and Nutrition Survey, more than 75% of Mexicans ignore the number of calories required daily [44]. This information is required to interpret GDA's correctly. This survey also reports that only 23% of the population reads the label, and that only 9.7% uses this information to make healthy choices [44]. In this line, some studies have reported that GDA understanding among Mexican population is poor, even among populations with higher education levels and nutrition knowledge [14-16].

Based on the former, the current front of pack labelling system needs to be revised to identify other labels that could be more effective than GDA's, based on a better acceptability and understanding.

This study aims to fill this gap of knowledge by providing scientific evidence on the acceptability and understanding of a variety of front of pack labelling systems. This evidence could be used by decision makers to design public policies related to front of pack labeling, as well as other researchers to design new research proposals.

## **5 OBJECTIVES**

---

### **5.1 GENERAL OBJECTIVE**

To design and evaluate Nutritional Front of Pack Labelling Systems for processed foods that are easy to understand by Mexican consumers to promote healthy food choices.

### **5.2 SPECIFIC OBJECTIVES**

1. To design alternatives of Front of Pack Labels that are easy to understand and useful in guiding healthy food choices among Mexican consumers.
  - a. To explore how several nutrient profiling systems classify a sample of food products currently available in the Mexican market.
  - b. To explore the acceptability and understanding of Front of Pack Labelling Systems used in the international food market in a sample of Mexican consumers living in urban areas.
  - c. To identify the graphic and language elements of the labelling systems that facilitate the understanding of the message of the labels towards healthy food selection.
  - d. To design Front of Pack labeling proposals considering the graphic and language elements identified in the previous step.
2. To identify which of the proposed labels has the best performance, in terms of acceptability and objective understanding, in a sample of Mexican consumers.

- a. To explore the acceptability and understanding of Front of Pack Labelling Systems used in the international food market in a sample of Mexican consumers living in urban areas.
3. To evaluate the efficacy of the two best labelling proposals to promote healthy food choices using an on-line shopping simulation in a sample of Mexican consumers.

## 6 HYPOTHESIS

---

A front of pack labelling system that takes into account the graphic and language elements considered by Mexican consumers as relevant for communicating the “healthy” message, will be effective in improving the nutritional quality of food choices during an on-line shopping simulation in this population.

## 7 METHODS

---

The study will be a cross-sectional type with a mixed-methods approach, meaning with qualitative and quantitative data collection and it will comprise three phases. Along the three stages, we will work in parallel with a graphic design team and an expert company in consumers researches in order to strength the research team and the resulting Front of Pack Labelling proposals of this Project.

### 7.1 PHASE 1. DESIGN OF FRONT OF PACK LABELLING PROPOSALS

This first phase of the project comprises three stages. The first stage intends to identify Front of Pack Labelling Systems currently used around the world. During the second stage the acceptability and understanding of the identified Front of Pack Labelling Systems proposals will be explored. The last stage will consist on the design of Front of Pack labelling proposals using the findings of the previous stages.

#### 7.1.1 Stage 1. Identification of Front of Pack Labelling and Nutrient Profiling Systems

##### 7.1.1.1 *Review of literature*

A scientific and gray literature research will be done to identify the Front of Pack Labelling Systems currently used around the world. From this first search, the research team will select by convenience the Front of Pack Labelling Systems to be explored in the next stage. All Front of Pack Labelling Systems currently used in Mexico and other Latin American countries will be included. In addition, Front of Pack Labelling Systems implemented in other countries that have shown effectiveness in improving healthy food choices will be selected. The final sample of Front of Pack Labelling Systems will not exceed a total of six systems, and will be representative of the main system categories: specific nutrients (for example: multiple or simple traffic light) and summary (for example Smart Choices). The selection will consider labelling systems that evaluate only negative aspects (such as fats, sugars and salt) of the food product, and those evaluating positive (such as fruit, vegetables, nuts or fiber content) and negative aspects.

In addition, a scientific literature research will be conducted to identify the nutrient profiling systems developed to date for the classification of food products based on their nutritional

content. The research team will select validated nutritional profiling systems and whose algorithm is public. The final sample of nutritional profiling systems will include those systems that consider only nutrients to limit as well as those that consider food to promote.

#### **7.1.1.2 Classification of products by nutrient profiling systems**

The performance of the identified nutrient profiling systems will be explored using a sample of food products currently available in the food market. The nutritional information of these products was collected as part of another research project included in the main research project. This data base has all collected information from 2014 to 2016

Classification exercises will be performed using STATA version 14.0. The following food categories will be included: 1) milk and dairy products, 2) sugary beverages, 3) salty snacks, 4) breakfast cereals, 5) ready to eat meals. The results will be evaluated by the research team, with expertise in nutrition, and will select the nutritional profiling system that better classifies food based on their nutritional content. Researchers will select three products of each food category. The nutritional content of these products should be different enough as to show a grading, from the healthiest to the least healthy. These foods will be used for the quantitative evaluation of acceptability and understanding of the labelling proposals.

#### **7.1.2 Stage 2. Understanding and acceptability of Front of Pack Nutritional Labelling Systems among Mexican consumers**

This stage comprises the assessment of the acceptability and understanding of the Front of Pack Nutritional Labelling systems selected in the previous stage. For that purpose, qualitative methodologies will be used (focus groups) aiming to explore the labels and to identify the graphic and language elements of the labelling systems that facilitate the communication of the central message of the labels. Qualitative methodologies are an ideal option to explore the consumers' perception regarding Front of pack labelling in depth [17]. Also, quantitative tools will be used to complement these areas.

Given that the research team lacks of a marketing background, which is needed to guide the focus groups in order to identify the desired graphic and language elements of the labels, as well as to comply with the timing of the project, focus groups will be led by the company Cuartel General de Comunicación y Estrategia SC (Headquarters of Communication and Strategy PP). The Company, hereinafter so-called Cuartel, has wide experience in marketing research through qualitative and quantitative methodologies. Cuartel has done more than 3000 studies in Communication, Image, Positioning, Use and Habits, Segmentation, Product testing, Proof of concept, Advertising evaluation, Price, satisfaction and loyalty. The Research team of the National Institute of Public Health will supervise the focus groups to ensure the fidelity of the methodology as well as the ethical principles of the research.

##### **7.1.2.1 Participants and y recruitment**

Initial contact and recruitment of participants will be done at different sale points, such as convenience stores, mini supers (Oxxo, Extra, 7 Seven), and retail stores located in different points of Mexico City. The selection of the sale points will be done by convenience, and will include those located in AGEBS (the Mexican equivalent for census tracts) classified as of intermediate socioeconomic level (3, 4 or 5) according to INEGI (National Institute of Statistic and Geography) [42].

An initial questionnaire will be used to explore eligibility criteria, including general demographic information (age, sex, information contact), consumption and purchase habits, as well as a series of questions to determine the individual socioeconomic level (Appendix 1). This rule is an algorithm developed by the Committee of Socioeconomic Levels and measures the extent in which the most important needs of households are satisfied by considering eight characteristics or possessions of the household and schooling of the person who most contributes to household expenses. The eight variables are: 1) schooling of the person who most contributes to expenses, 2) number of rooms, 3) number of bathrooms, 4) number of lamps/bulbs, 5) number of automobiles, 6) possession of a shower, 7) possession of a stove, and 8) Type of flooring. As a result, this rule produces an index that ranks households into seven levels, from A (highest socioeconomic level) to E (lowest socioeconomic level).

The questionnaire will be applied randomly with a systematic skip (every 5 consumers) at the exit of the sale point, after a brief explanation of the study objectives and informed consent. Participants classified as typical C or lower C and meeting inclusion criteria will be invited to participate in focus groups (see below).

There will be a total of five focus groups with an average of 5 to 10 participants each, which often buy and consume (twice a week), at least two of the categories of prepackaged meals and bottled beverages of interest for the study (mentioned in section 8.1.1.2) and meet the following inclusion criteria:

- **Group 1:** Men and women 13 to 15 years old that visit the sales point by themselves, with a specific budget to purchase products.
- **Group 2:** Men and women 21 to 23 years old, who visit the sales point at least twice a week, purchase these types of foods and/or beverages, for their own consumption and/or their family.
- **Group 3:** Women, mothers of 3 to 12 year old children who visit the sales point at least twice a week, purchase these types of foods and/or beverages, for their own consumption and/or their family.
- **Group 4:** Men, fathers of 3 to 12 year old children who visit the sales point at least twice a week, purchase these types of foods and/or beverages, for their own consumption and/or their family.
- **Group 5:** Men and women 55 to 70 years old who visit the sales point at least twice a week, purchase these types of foods and/or beverages, for their own consumption and/or their family.

Group 1 participants (Men and women from 13 to 15 years) will be contacted only if they attend the recruitment points accompanied by a parent or guardian. Participants who meet the inclusion criteria will be invited to participate voluntarily in the focus groups, indicating the day, time, place and duration of the event, as well as the incentive they will receive in return for their participation. Candidates who agree to participate in the study will receive at least three reminders via text message or phone call about the date and location of the focus groups. Group 1 participants will be asked to attend with a parent or guardian.

### **7.1.2.2 Materials to evaluate label understanding and acceptability**

The graphic design team will be asked to develop each of the Front of Pack labelling proposals in the following versions:

- a) Amplified option: Labels will be printed out in double letter size to explore the communication elements of each label (information, figures or hard data, texts, typography, colors, iconography, etc.).
- b) Real size: Real size food product dummies will be prepared to evaluate label understanding and acceptability. Dummies will reproduce real food products currently available on the Mexican market. These products will represent a range of foods with a gradient of nutritional quality (for example from the healthiest to the least healthy). Food selection will be done considering the categories previously mentioned and based on the food classification exercise done during the first stage of this phase of the study (section 8.1.1.2).  
Dummies will present all the elements of the frontal part of the package of real products, including other nutritional quality labels (such as nutritional or health declarations). However, other front-of-pack labeling system will be eliminated (for example GDA's or the Mexican "Distintivo Nutricional").
- c) Competitive environment: An image of store shelves or racks will be printed to evaluate the understanding and acceptability in a competitive environment. The image will present real food packages displaying one of the various labeling systems.

The first focus group to be implemented will also work as a pilot group. Based on this experience the required methodological and time adjustments will be made. Treatment and dedication to this first group will be similar to the rest of the focus groups, including moderation of the focus group, audio and video recording of the session, audio transcription, information analysis and final results.

### **7.1.2.3 Procedures for data collection**

#### **7.1.2.3.1 Qualitative Information**

Information will be collected according consumers' perspective using focus groups. Data on the different categories of the processes of interpretation of the label and the decision making on food selection will be collected. These categories were carefully selected considering previous experiences on the design of Front of Pack Labelling Systems [21], as well as the conceptual framework of acceptability of systems proposed by Nielsen (18). The Guide of Topics for the Focus Group is structured according these categories:

- a) Perceptions towards Front of Pack Labelling, food selection and health. Knowledge, attitudes, intentions and behaviors related to Front of Pack Labelling, food selection and health.
- b) Acceptability of the different alternatives of Front of Pack Labelling, both in their amplified size and real size, considering the following items:
  - a. Liking of labels
  - b. Attractiveness of labels
  - c. Cognitive load of label processing

- c) Objective understanding of the different alternatives of Front of Pack Labelling, both in their amplified size and real size, considering the following items:
  - a. Ability to understand the design elements
  - b. Ability to understand the main message
- d) Usefulness of the different alternatives of Front of Pack Labelling, both in their amplified size and real size, considering the following items:
  - a. Useful utility
  - b. Motivational relevance
  - c. Message for action
- e) Graphic and language elements that facilitate the understanding of the message towards the selection of healthy foods, considering the following items:
  - a. Size of the texts
  - b. Information
  - c. Typography
  - d. Colors
  - e. Iconography
  - f. Ideal Front of Pack Labelling

Focus groups will have a duration of approximately two hours, and will be video and audio recorded in a digital file for its posterior transcription, codification and analysis. Before the focus groups starts, participants' informed consent to participate on the Project and to record the session will be obtained. The informed consent meets the AMAI ethics, information management politics and Cuartel's privacy terms, as well as the guidelines established by the Ethics Committee of the National Institute of Public Health (Appendix 2). Subsequently, the Guide of Topics will be applied for the Focus Group (Appendix 3).

#### **7.1.2.3.2 Quantitative Information**

Once the focus group Guide has been completed, a questionnaire evaluating the acceptability and understanding of the different FoPNL Systems will be applied (See Appendixes). The questionnaire has been designed considering the different aspects that determine the acceptability of a system (18), as well as previous experiences recently published exploring acceptability and understanding of a new proposal of Front of Pack Labelling in European consumers [21]. The questionnaire consists of 26 items divided in three sections: 1) Demographic Information. 2) Acceptability of the FoPNL Systems proposals, and 3) Objective understanding of the Front of Pack Labelling.

**Acceptability:** Participants will be asked to select the label that best corresponds to a series of affirmations. A total of four items will evaluate liking of the label, three items will evaluate the attractiveness of the label, and four items will explore perceived cognitive load.

**Objective Understanding.** Participants will classify three products according to their nutritional quality, using the different FoPNL systems evaluated. For this purpose, images of three products of the same food category (previously selected during the exercises with the nutritional profiling system) displaying one of the FoPNL will be shown. Participants will classify the products according to their nutritional quality. No other nutritional information will be provided. The classification will be considered correct if all three products are ranked

in the expected order, based on their nutritional quality. The same five food categories used in the exercises of nutritional profiling explained in section 8.1.1.2 will be tested.

**Demographic Information.** Basic Information of age, sex, occupation, civil status, having children, schooling, interest in health, chronic diseases, as well as the geographical region of the participant using the zip code will be collected. In addition, questions used in the National Survey of Health and Nutrition 2016 will be included to collect information on socioeconomic level. For this questionnaire, the following 8 items will be considered to estimate the level of welfare condition of the participants: flooring, walls and ceiling material, number of rooms for sleeping, water supply, automobile possession, number of household goods (refrigerator, washing machine, microwave, stove, water heater), and the number of electronic appliances (television, radio, telephone, computer).

#### **7.1.2.4 Incentive**

At the end of the focus group, an electronic purse of the Walmart group of a value of \$400.00 Mexican pesos will be awarded as remuneration for their participation on the Project.

#### **7.1.2.5 Fieldwork**

Focus groups will be led by previously trained personnel in leadership of focus groups. Two researchers with wide experience in qualitative methodologies will be involved in the moderation and analysis of the information obtained: one of the researchers will be in front of the group conducting the research dynamics, while the other one will remain behind Gesell dome observing the conduction of the groups, reactions of the interviewees and the whole verbal and not verbal language that us generated. The researcher behind Gesell dome will send notes to the moderator when considered necessary or when an investigator from the INSP considers necessary to investigate into a subject.

#### **7.1.2.6 Data analysis**

##### **7.1.2.6.1 Analysis of quantitative data**

The analysis will be carried out using the statistical package Stata version 14. Descriptive tabulation of demographic data will be made through an estimation of means and standard deviations (or medians and interquartile ranges in case of variables with non-parametric distribution) for quantitative variables, as well as proportions for categorical variables.

To evaluate label acceptability, the percentage of participants who selected each one of the proposed labels in relation to liking, attractiveness and perceived cognitive load of the label will be calculated. To compare the performance of the label in respect to objective understanding, the percentage of correct responses by labelling system, will be calculated. These ratios will be calculated also by food category and by sub-groups (for example, schooling, sex). The differences by category will be explored using Chi square tests.

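### A chi-square test by sex on the Phase 1 and 2 questionnaires can mistake a difference between discussion groups for a sex difference, because two of the five groups are single-sex and the plan makes no allowance for group (minor)

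*Combined protocol and SAP*

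**What the plan says.** All references are to the combined protocol and SAP.

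- **Groups (7.1.2.1).** "There will be a total of five focus groups with an average of 5 to 10 participants each". Groups 1, 2 and 5 are mixed-sex and defined by age (13 to 15, 21 to 23, 55 to 70). Group 3 is "Women, mothers of 3 to 12 year old children"; Group 4 is the corresponding group of fathers.
- **Discussion (7.1.2.3.1).** Each session lasts roughly two hours. The topic guide covers acceptability and objective understanding of the labels.
- **Timing (7.1.2.3.2).** "Once the focus group Guide has been completed, a questionnaire evaluating the acceptability and understanding of the different FoPNL Systems will be applied". The questionnaire therefore measures what the group has just discussed.
- **Analysis (7.1.2.6.1).** Percentages are computed by labelling system. Then: "These ratios will be calculated also by food category and by sub-groups (for example, schooling, sex", followed by "The differences by category will be explored using Chi square tests".
- **Phase 2 (7.2.1)** uses the same methodology.

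No section names the focus group as a stratum, cluster or covariate. No significance level or ICC is given for this analysis.

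**The concern.** A Pearson chi-square assumes that respondents are independent. Here they have discussed the labels together before answering. Two further features could make groups differ in procedure: the first group doubles as a pilot, after which methods and timing may be adjusted (7.1.2.2), and an observer may send notes to the moderator during a session (7.1.2.5).

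Reducing the data to one answer per person does not remove this dependence. The mothers' group enters the female side of a sex comparison whole, and the fathers' group enters the male side whole. Whatever separates those two discussions is counted as a sex effect. At stake is a statement that women and men understand or accept a label differently when only two conversations differed.

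**Working it through.** The plan has no figure of its own to reproduce here: it gives no sample size, power, alpha or ICC for the questionnaire.

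**Inputs from the documents.** Five groups of m = 5 to 10, so 25 to 50 people; Group 3 all women; Group 4 all men; Groups 1, 2 and 5 mixed.

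**Assumptions.** Equal group sizes; mixed groups about half women; one binary answer per person; 50% correct; no true sex effect; two-sided 5% level (stated only for Phase 3, in 7.3.6); ICC from 0 to 0.3.

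**Step 1: variance of the sex difference.** Let w be a group's share of all women minus its share of all men. Relative to the independence variance, the true variance is

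1 − ICC + ICC × Σw² / (1/nF + 1/nM).

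Each sex has 2.5m people. So w = m/2.5m = 0.4 for Group 3, −0.4 for Group 4 and 0 for the mixed groups.

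- Σw² = 0.16 + 0.16 = 0.32.
- 1/nF + 1/nM = 2/(2.5m) = 0.8/m.
- The quotient is 0.4m, so the ratio is 1 + ICC × (0.4m − 1).

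That is 1 + ICC for m = 5, 1 + 2.2 × ICC for m = 8 and 1 + 3 × ICC for m = 10. It exceeds 1 for any positive ICC at these sizes. At ICC 0.2 the ratios are 1.20, 1.44 and 1.60. With true alpha = 2 × [1 − Φ(1.96/√ratio)], these give 7.4%, 10.2% and 12.1%.

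**Step 2: simulation.** Group probabilities were drawn from a beta distribution, with 40,000 data sets per cell and the uncorrected Pearson chi-square by sex. With 5 per group, the mixed groups split 2 and 3. Rejection rates were:

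| ICC | 5 per group | 8 per group | 10 per group |
|---|---|---|---|
| 0 | 5% | 4% | 6.5% |
| 0.05 | 5% | 6% | 9% |
| 0.1 | 6% | 7% | 11% |
| 0.2 | 8% | 10% | 15% |
| 0.3 | 10% | 14% | 20% |

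The 6.5% at ICC 0 with 10 per group comes from the discreteness of small tables, so not all of that column's excess is clustering.

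**Step 3: other factors.** Schooling was tried with the 13 to 15 year olds all low and the other groups split evenly: rejection reached at most about 8% at ICC 0.3. For a factor split evenly within every group, the test became conservative, 2.3% to 3.0% at ICC 0.3.

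**Step 4: stratifying by focus group.** A Cochran-Mantel-Haenszel test for sex rejected 4.0% to 5.5% of the time across the settings tried. It uses only the mixed groups: 3 × 5 = 15 to 3 × 10 = 30 people. For an illustrative 50% versus 80% correct with n per sex, approximate power is

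Φ{[0.3 − 1.96 × √(2 × 0.65 × 0.35/n)] / √[(0.25 + 0.16)/n]}.

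- Groups of 5: n falls from 12.5 to 7.5 and power from 0.34 to 0.22.
- Groups of 10: n falls from 25 to 15 and power from 0.61 to 0.40.

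The higher figures treat all respondents as independent, so they flatter the unstratified test.

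**The case against.** **The sub-group tests may not exist.** The sentence on chi-square tests refers to differences by category, and the preceding sentence uses that word for food category. The plan could intend percentages by sub-group and tests by food category only. This stands as an ambiguity. Because sub-groups are named in the same preceding sentence, reading the tests as covering them is natural but not certain.

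**The ICC is assumed.** This also stands. With 5 per group and an ICC of 0.05 the sex test is close to nominal.

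**A reader might infer that every sub-group test is inflated, and severely.** The documents do not support that. Section 7.1.2.6.1 names schooling and sex only, and schooling is little affected. A comparison of the mothers' and fathers' groups with the rest would reject 14% to 30% of the time (8 per group, ICC 0.1 to 0.3), but the plan names no such test. Its sub-group list is open-ended and age and having children are collected, so the confounding is worth stating; that figure should not be used to size this point.

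**A reader might also infer that false sub-group findings will steer the redesign or the choice of labels.** No section says so. Section 7.1.3 relies on language and design elements, and 7.2.2 picks the two labels best evaluated for acceptability and understanding, which is a comparison between labels. No specific objective in 5.2 asks who understands which label, and section 9 already disclaims representativeness.

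What remains is that a test by sex, one of the plan's own examples, has the wrong error rate whenever answers within a group are positively correlated.

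**Conclusion.** The concern holds for sex, at minor severity. On the natural reading of 7.1.2.6.1, the unstratified chi-square can present a difference between discussion groups as a sex difference, even with one answer per person. The error rate ranges from about nominal (5 per group, ICC 0.05) to about 20% (10 per group, ICC 0.3). It rests on an ICC that the documents do not give, equal group sizes and evenly split mixed groups.

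If age or parenthood were tested, the sub-group would coincide wholly or largely with particular focus groups, and the two could not be separated by any analysis. The comparisons are exploratory, involve about 25 to 50 people per phase, and leave the Phase 3 randomised comparison unaffected.

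**What to change.** Amend 7.1.2.6.1, which then carries into Phase 2 through 7.2.1:

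1. State which comparisons the chi-square tests cover.
2. By default, report sub-group percentages without p-values, and say that sub-group and discussion group are partly or wholly confounded.
3. If a test by sex or schooling is kept, stratify it by focus group. Use an exact or Cochran-Mantel-Haenszel test for a binary result per person, or a stratified rank test for a per-person count of correct rankings. The second matters because each person ranks products for several labels and five food categories (7.1.2.3.2).
4. Give no p-value where the sub-group coincides with whole focus groups.

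Cluster-robust standard errors are not a dependable substitute with only five groups.

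**Cost.** Wording only; no change to data collection. The price is information: a stratified sex test draws on about 15 to 30 people, with power of roughly 0.22 to 0.40 for 50% versus 80% correct, and some sub-groups get no test. For an exploratory stage, the descriptive default is the simpler choice.
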